1.2.2.2. Plaque Psoriasis

The tofacitinib development program in patients with moderate to severe chronic plaque psoriasis was comprised of 2 Phase 3 randomized, placebo-controlled studies (A3921078 and A3921079), 1 Phase 3 placebo-controlled active comparator study (A3921080), 1 Phase 3 withdrawal/retreatment study (A3921111) and 1 Phase 3 open-label LTE study (A3921061). The primary efficacy outcomes in the program included the proportion of patients with a Physician's Global Assessment (PGA) response of "clear" or "almost clear" and the

proportion of patients with at least a 75% reduction in Psoriasis Area and Severity Index (PASI) relative to baseline (ie, PASI75) response.

Tofacitinib 5 mg BID or 10 mg BID treatment resulted in consistent and significant improvement in multiple variables:

- Clinically meaningful improvements in the PGA response of “clear” or “almost clear” and PASI75 response were demonstrated in the tofacitinib 5 mg BID and 10 mg BID dose groups relative to placebo. In studies A3921078 and A3921079, the PGA and PASI75 response rate were statistically superior to placebo at the 16-week primary time point.
- Tofacitinib 10 mg BID was statistically significantly superior to placebo and non-inferior to high-dose etanercept (50 mg twice weekly subcutaneously) at 12 weeks in the PGA and PASI75 responses in study A3921080.

Additional information on completed and ongoing psoriasis studies can be found in the current version of the tofacitinib Investigator’s Brochure.

1.2.2.3. Phase 3 PsA Studies

The tofacitinib Phase 3 program was designed to evaluate the efficacy of tofacitinib 5 mg BID and 10 mg BID in patients with active PsA. The 2 tofacitinib Phase 3 pivotal studies (A3921091 and A3921125) compared the efficacy of both tofacitinib doses to that of placebo over 3 months for improvements in multiple PsA domains, examined the onset of efficacy, and assessed the persistence of efficacy of both tofacitinib doses in conventional synthetic disease-modifying anti-rheumatic drug-inadequate responder (csDMARD-IR) TNFi-naïve and TNFi-IR populations. All study participants randomized to placebo were advanced in a blinded fashion at Month 3 to either tofacitinib 5 mg BID or 10 mg BID and treatment duration was a total of 12 months in A3921091 and 6 months in A3921125.

The first Phase 3 PsA study, A3921091 has completed and the primary endpoints were met. The American College of Rheumatology 20% response rate (ACR20) was statistically significantly greater for both tofacitinib 5 mg BID and 10 mg BID dose treatment groups than the placebo treatment group at Month 3. The mean change from baseline (decrease) in the Health Assessment Questionnaire-Disability Index (HAQ-DI) was statistically significantly greater than placebo for both tofacitinib 5 mg BID and 10 mg BID dose treatment groups at Month 3. Evidence of efficacy was also observed across other PsA domains (secondary endpoints) and was maintained to Month 12.¹⁰

Results from the second Phase 3 PsA study, A3921125 demonstrated that there were significantly greater improvements in ACR20 response rate and Δ HAQ-DI for both doses versus placebo; improvement persisted to Month 6.¹¹

1.2.3. Summary of Safety

The clinical development program for oral tofacitinib includes healthy volunteers and subjects with RA, plaque psoriasis, inflammatory bowel disease (Crohn's disease and ulcerative colitis), ankylosing spondylitis, psoriatic arthritis and renal transplants enrolled in Phase 1, 2 and 3 studies.

Over 22,000 subjects have received at least one oral dose of tofacitinib in a clinical trial as of January 2016. Of these, approximately 8700 subjects have continued clinical trial participation by enrolling in long-term extension studies or other types of continuation studies.

Potential safety risks for subjects treated with tofacitinib are based on the totality of the data including nonclinical and clinical data across the entire tofacitinib development program with the majority of clinical data coming from studies in RA and PsO patient populations, including open-label extension studies. These risks include serious and other important infections such as tuberculosis, opportunistic infections and herpes zoster (HZ) infections, potential for malignancies including lymphoma, and the potential for gastrointestinal (GI) perforations. Subjects receiving tofacitinib may be at increased risk for non-melanoma skin cancer (NMSC). Based on nonclinical data, there is potential for tofacitinib to have effects on pregnancy and the fetus.

It has long been recognized that RA is associated with accelerated atherosclerosis and increased cardiovascular (CV) mortality and morbidity. The incidence of CV events during treatment with tofacitinib in RA patients was evaluated by an independent, external CV adjudication committee. No evidence of heightened CV risk was found. Tofacitinib was not associated with an increase in adjudicated CV events within the PsO development program.

Interstitial lung disease (ILD) is a serious comorbidity in RA patients. Risk factors for the development of ILD in RA include Asian race, older age, male gender, higher RA disease activity and treatment with corticosteroids or MTX. The incidence rate of ILD and geographic variation seen in patients treated with tofacitinib are consistent with what has been reported in literature. For additional information, please refer to Section 6.2.3.1.5 of the IB.

Laboratory changes associated with the oral use of tofacitinib treatment in humans include decreases in hemoglobin levels, absolute neutrophil counts (ANC), and absolute lymphocyte count, increases in total cholesterol, HDL cholesterol, LDL cholesterol, transaminases, serum creatinine, and creatine kinase (CK). Recovery of laboratory changes upon discontinuation of tofacitinib treatment is characteristically observed. The safety profile of tofacitinib in both rheumatoid arthritis and psoriasis subject populations is qualitatively similar. The current safety profile for the treatment of PsA across both studies, A3921091 and A3921125 is similar to that reported for RA and no new risks have been identified.^{10,11}

Interpretation of these results and the possible risks associated with the administration of tofacitinib are summarized in [Section 6.2.3](#) (Special Safety) and [Section 7](#) (Summary of Data and Guidance for the Investigator) of the Investigator's Brochure.

1.2.4. Overall Risk-Benefit

1.2.4.1. Potential Benefits

Given the chronic nature of this disorder and the limited available therapies, there remains an unmet medical need for an effective oral treatment for PsA.

The benefits to individual subjects participating in this study will be the potential continued control of their PsA disease activity including rheumatological signs and symptoms (eg, joint swelling/tenderness, enthesitis, dactylitis and spondylitis), dermatological manifestations (eg, skin plaques), physical function and fatigue. All subjects may also benefit from gaining knowledge about their health status through study tests and physician assessments, as well as having close monitoring of their disease.

1.2.4.2. Potential Risks

The risks associated with tofacitinib are similar to the risks associated with the use of other immunosuppressive agents, including a potential increased risk for serious and other important infections, eg, tuberculosis and viral reactivation such as herpes zoster. In the RA program, the serious infection rate in tofacitinib-treated subjects was consistent with the rates of serious infections in patients treated with other therapeutic interventions including biologic DMARDs. In the PsO program the serious infections overall rate was lower than was observed for the RA program. Serious infections were more frequent among the elderly (>65 years), subjects with diabetes mellitus and subjects treated previously with biological agents. Caution is also recommended in subject with a history of chronic lung disease as these patients may be more prone to infections. Rates of herpes zoster infections in tofacitinib-treated subjects with RA were increased compared with placebo-treated RA subjects and historical controls; this included an increased risk of herpes zoster infections in Asian RA patients compared with non-Asian RA patients. In the tofacitinib RA clinical development program, the rate of HZ varied significantly across countries and regions. The incidence rates of HZ in Japan and Korea were notably higher than the rates observed in other regions/countries. The reason for the increased risk of HZ in Japan and Korea is unclear.

Decreases in white blood cell counts, particularly neutrophils and lymphocytes, and decreases in hemoglobin have been observed. These effects were usually mild to moderate and returned to normal after discontinuation of therapy. Anemia is a possible consequence of JAK2 inhibition. Experience to date indicates that anemia is easily monitored, usually manageable without discontinuation of drug, and reversible upon discontinuation of tofacitinib. Neutropenia is of primary concern by virtue of its relationship to an increased risk of infection. Thus far, no association between the occurrence of neutropenia and infection has been observed in the tofacitinib program.

Cases of GI perforation were observed in RA subjects taking tofacitinib, often in the setting of diverticulitis. All affected subjects had underlying risk factors, including a history of concomitant drug treatment with non-steroidal anti-inflammatory drugs (NSAIDs) and/or corticosteroids that have been associated with an increased risk of GI tract injury.^{12,13} Isolated events of gastrointestinal perforation have also been reported in clinical trials in other tofacitinib indications including one (preferred term: appendicitis) in the A3921091 study.

ILD, a complex co-morbidity in RA patients, has also been reported in RA patients receiving tofacitinib. While data from the RA development program do not identify a pulmonary toxicity for tofacitinib, an increased risk of ILD was observed in Asian RA patients as compared to non-Asian RA patients but there was no consistent dose relationship.

Based on nonclinical data, there is a potential risk for teratogenicity with tofacitinib.

A more detailed discussion of tofacitinib safety can be found in the Investigator's Brochure in Section 6.2.3.

1.2.5. Clinical Pharmacokinetics

The pharmacokinetic (PK) profile of tofacitinib is characterized by rapid absorption, rapid elimination (terminal half-life of ~3 hours) and dose proportional PK. Co-administration with a high fat meal increased the tofacitinib AUC by 14% and decreased C_{max} by 26%; no dosage adjustments or meal restrictions during chronic dosing are warranted. The clearance mechanisms for tofacitinib in humans appear to be both non-renal and renal excretion of the parent drug, the former accounting for approximately 2/3 of the total clearance. The

metabolism of tofacitinib appears to be primarily mediated by CYP3A4 with minor contribution from CYP2C19 as suggested by data from poor metabolizers of CYP2C19. The PK of tofacitinib is similar between Caucasians and Japanese healthy volunteers.

In vitro studies have shown that tofacitinib does not significantly inhibit the major drug metabolizing CYPs, indicating a low potential for tofacitinib to increase the exposure of other drugs. This was demonstrated in a clinical study where tofacitinib did not have an effect on the pharmacokinetics of an oral dose of midazolam (a highly sensitive CYP3A substrate) in healthy volunteers. On the other hand, inhibitors and inducers of CYP3A4/5 are likely to alter the disposition of tofacitinib. Co-administration of tofacitinib with fluconazole, a moderately potent inhibitor of CYP3A4 and a potent inhibitor of CYP2C19, resulted in 79% and 27% increases in the AUC and C_{max} of tofacitinib, respectively. Co-administration of tofacitinib with methotrexate had no effect on the PK of tofacitinib and resulted in an approximate 10% decrease in the AUC of methotrexate. The extent of decrease in methotrexate exposure does not warrant modifications to the individualized dosing of methotrexate. Co-administration of tofacitinib with cyclosporine and oral tacrolimus, moderate and weak CYP3A4 inhibitors, respectively, resulted in increases of 73% and 21% in AUC_{inf} of tofacitinib. In both cases, tofacitinib C_{max} was decreased slightly; ratio 91%, for tacrolimus and 83%, for cyclosporine.

Consistent with the ~30% contribution of renal clearance to the total clearance of tofacitinib, mean exposure in end stage renal disease (ESRD) subjects (on a non-dialysis day) was approximately 40% higher compared with historical healthy subject data. In contrast, in a separate study, mean exposure was approximately 125% higher in subjects with severe renal impairment compared with healthy subjects. Mild and moderate renally impaired subjects had 37% and 43% higher exposure, respectively, compared with healthy subjects.

Based on these data, subjects with estimated creatinine clearance <40 mL/min will be excluded from this study as will concomitant use of moderate to potent inhibitors of CYP3A4/5.

Further clinical pharmacology background information on tofacitinib can be found in the current version of the tofacitinib Investigator's Brochure.

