- Subjects who are qualified to enter A3921092 extension study and do so >14 days (but ≤3 months) after early termination or end of study (EOS) visit in qualifying study must undergo re-screening procedures and have separate visit for baseline activities. Baseline visit must occur 2-28 days after Screening visit.
- Subjects who are qualified to enter A3921092 extension study and do at the end of study (EOS) visit in qualifying study do not need to be rescreened or have an additional baseline visit.

3. Subjects who are qualified to enter A3921092 extension study and do not do so at the end of study (EOS) visit but <14 days after early termination or EOS in parent study do not need to be re-screened but require procedures performed for baseline.
4. For those subjects that complete the study, follow-up phone call will be made to subjects within 7 days after the 28 days following EOS visit and adverse events noted.
5. If a subject discontinues from the study due to abnormal hematology or clinical chemistry results which meet criteria as described in [Appendix 4](#), or discontinues due to an adverse event, a follow-up visit must be performed after the Early Termination visit within 28 days (± 7 days) of last dose of study treatment.
6. Disease Activity Assessment must be performed on subjects who enroll >14 days after end of study visit in qualifying study to determine if subject has sufficient evidence of PsA disease activity to warrant use of tofacitinib as a DMARD ([Section 7.1.1](#)).
7. Cardiovascular (CV) Risk Factor Assessment includes multiple assessments such as smoking status, average weekly alcohol consumption, and family history of premature coronary heart disease (CHD) (See [Section 7.4](#) for complete list).
8. Complete physical exam should be performed annually (Month 12, 24 and 36) and includes: height, weight, general appearance, skin, HEENT (head, eyes, ears, nose and throat), heart, lungs, abdomen, lower extremities, neurologic and lymph nodes. Targeted physical exam should be performed at other scheduled visits and includes: weight, examination of heart, lungs, abdomen, lower extremities (for peripheral edema) and lymph nodes.
9. 12-lead ECG will be taken at annual visits (Month 12, 24 and 36) and Early Termination (ET) visit only. ECG will be evaluated by a central reader.

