3. STUDY DESIGN

This is a Phase 3, long-term, open-label extension study designed to evaluate the safety, tolerability and efficacy of tofacitinib in subjects with active PsA who have previously participated in randomized PsA clinical studies with tofacitinib. For subjects who complete participation in such a randomized clinical study with tofacitinib, the final visit of the qualifying study can be combined with the screening and baseline visit for this study. Additional assessments and inclusion/exclusion criteria are required for subjects who enroll >14 days after completing treatment in their qualifying study. In this case, a separate screening visit to determine subject eligibility is required followed by a baseline visit.

All eligible subjects from qualifying studies A3921091 and A3921125 will receive open-label tofacitinib 5 mg BID upon entry into A3921092. Subjects from A3921091 will receive first dose of study medication ≥ 1 week after last injection of study medication in that qualifying study. Tofacitinib dose may be increased to 10 mg BID at study visits if, based upon investigator's discretion, subjects receiving tofacitinib 5 mg BID would benefit from a higher dose and are not experiencing any tofacitinib-related adverse events, including abnormalities in laboratory parameters that are judged to be related to tofacitinib. Tofacitinib dose may be decreased (ie, 10 mg BID to 5 mg BID) for safety reasons at any time during the study. Treatment duration for subjects participating in the LTE study is approximately 3 years (36 standardized 4-week months). Subjects participating in the sub-study may have up to an additional 1 year (12 standardized 4-week months) of treatment for a maximum potential total of approximately 4 years (48 standardized 4-week months).

At various time points in this trial, safety measurements, including physical examination, clinical laboratory tests, adverse event monitoring, electrocardiograms (ECGs) and vital signs will be performed. All subjects will be monitored for clinical evidence of response of PsA to treatment. Health Outcome Measures (ie, Patient Reported Outcomes assessment questionnaires for pain, quality of life, physical function, fatigue, work limitations, health care resource utilization and health status) will also be performed at various time points in this trial. In addition, subjects will be monitored for serious infections, lymphadenopathy and lymphoproliferative disorder (LPD).

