4.2.1. Exclusion Criteria that Apply to All Subjects

1. Currently have non-plaque forms of psoriasis, eg erythrodermic, guttate or pustular, with the exception of nail psoriasis, which is allowed.
2. Subjects who are investigational site staff members directly involved in the conduct of the trial and their family members, site staff members otherwise supervised by the investigator, or subjects who are Pfizer employees, including their family members, directly involved in the conduct of the trial.

3. Pregnant females, breastfeeding females and females of child-bearing potential who are unwilling or unable to use a highly effective method(s) of contraception as outlined in this protocol for the duration of the study and for at least one ovulatory cycle after last dose of investigational product or females planning pregnancy. Women of childbearing potential must test negative for pregnancy prior to enrollment in this study. Subjects in Canada who are women of child-bearing potential, and sexually active, are required to use one highly effective method and one additional effective method of contraception (see [Appendix 9](#)). (Further description of the requirements and a list of contraceptives considered highly effective and acceptable for use in this study will be found in [Section 4.4.6](#)).
4. Current or recent history of uncontrolled renal, hepatic, hematological, gastrointestinal, metabolic (including hypercholesterolemia), endocrine, pulmonary, cardiovascular, or neurologic disease.
5. History of any autoimmune rheumatic disease other than PsA (including systemic lupus erythematosus, mixed connective tissue disease, scleroderma, polymyositis) or known diagnosis of fibromyalgia, without approval by Sponsor. Also excluded are subjects with prior history of, or current, rheumatic inflammatory disease other than PsA (eg, gout, reactive arthritis, chronic Lyme disease) without approval by Sponsor.
6. A subject with known immunodeficiency disorder or a first degree relative with a hereditary immunodeficiency.
7. Functional Class IV status as defined by the American College of Rheumatology classification of functional status for RA, ie, limited in ability to perform usual self-care, vocational and avocational activities.¹⁵
8. History of an infected joint prosthesis at any time, with the prosthesis still in situ.

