17. A subject requiring prohibited concomitant medications (See [Appendix 3](#)). For a medical condition in which it is important for the subject's safety to continue a prohibited drug described in [Appendix 3](#), and there is no study-permitted alternative, the subject must not participate in this study. Subjects receiving non-prohibited concomitant medications must be on a stable regimen which is defined as not starting a new drug or changing dosage within seven days or 5 half-lives (whichever is longer) prior to the baseline visit.
18. A subject known to be infected with human immunodeficiency virus (HIV), hepatitis B virus or hepatitis C virus or any chronic infection.
 - HBsAg⁺ is exclusionary; subjects who are HBsAg⁻ but HBcAb⁺ must undergo further testing and be HBsAb⁺ to be considered for enrollment.
 - Subjects who are HCV Ab⁺ must undergo further testing for HCV RNA and are allowed to enroll if negative.
19. A subject with evidence of skin conditions (eg, eczema) at the time of the screening or baseline visit that would interfere with evaluation of psoriasis.
20. Other severe acute or chronic medical or psychiatric condition or laboratory abnormality that may increase the risk associated with study participation or investigational product administration or may interfere with the interpretation of study results and, in judgement of investigator, would make subject inappropriate for entry into this study.

21. A subject who, in the opinion of the investigator or Pfizer (or designee), will be uncooperative or unable to comply with study procedures.
22. Participation in other studies involving investigational drug(s) (Phases 1-4) during study participation.

4.2.2. Exclusion Criteria That Apply to Subjects Who Enroll Into This Study After the 14 Day Window From the End of Study Visit of the Qualifying Study

Laboratory assessments at the Screening Visit or within 3 months prior to the baseline visit include:

- Evidence of hematopoietic disorders or evidence of hemoglobin levels <10 g/dL;
- An absolute white blood cell (WBC) count of <3.0 x 10⁹/L (<3000/mm³);
- Absolute neutrophil count of ≤1.5 x 10⁹/L (≤1500/mm³);
- Absolute lymphocyte count <1.0 x 10⁹/L (<1000/mm³);
- Platelet count <100 x 10⁹/L (<100,000/mm³).

Laboratory assessments at the Screening Visit only:

- Estimated creatinine clearance <40 mL/min by Cockcroft Gault equation ([Appendix 2](#));

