6.1.2. Subjects with Combined End of Study Visit/Baseline Visit

For subjects combining the End of Study (EOS) Visit from qualifying study with Screening/Baseline visit for A3921092, subjects must complete activities as indicated from EOS visit and the following procedures:

- Informed consent obtained.
- Register for subject identification number.
- Dispense study medication/schedule next visit.

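### The renal exclusion stated for the whole study (creatinine clearance <40 mL/min) is applied numerically only to subjects who enrol more than 14 days after the qualifying study

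*Protocol*

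**What the plan says.** Protocol Section 1.2.5 reports tofacitinib exposure by renal function. "Mild and moderate renally impaired subjects had 37% and 43% higher exposure" than healthy subjects, and severe impairment raised mean exposure by about 125%. From these data it concludes that "subjects with estimated creatinine clearance <40 mL/min will be excluded from this study". The same sentence also excludes moderate to potent CYP3A4/5 inhibitors. No entry route is singled out.

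The operative criteria are these:

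- **Section 4.2.2**, which applies only to subjects enrolling after the 14-day window, lists "Estimated creatinine clearance <40 mL/min by Cockcroft Gault equation", assessed at the Screening Visit only.
- **Section 3** announces the two-tier approach: "Additional assessments and inclusion/exclusion criteria are required for subjects who enroll >14 days" after finishing treatment in the qualifying study.
- **Section 4.2.1**, for all subjects, has #4, "Current or recent history of uncontrolled renal, hepatic, hematological, gastrointestinal, metabolic" and other listed disease, and #20, which includes a "laboratory abnormality that may increase the risk associated with study participation" subject to the investigator's judgement. Neither carries a renal number.
- **Table 1** footnotes say that subjects entering at the end-of-study visit "do not need to be rescreened or have an additional baseline visit". **Section 6.1.2** lists what is added at that visit: consent, registration and "Dispense study medication/schedule next visit".
- **Section 6.1.3** has chemistry drawn at a separate visit within 14 days but attaches no renal threshold to it.

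**The concern.** The protocol derives a safety exclusion from its own pharmacokinetic data and states it for the whole study, but the entry criteria enforce it on one route only. A subject already below 40 mL/min who rolls over directly can start open-label treatment planned for about 3 years with no numeric renal check.

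A limit in the qualifying studies, if there was one, would not fully close the gap. It would have been checked at entry to studies lasting 12 months (A3921091) or 6 months (A3921125), and Sections 1.2.3 and 1.2.4.2 report that tofacitinib raises serum creatinine. Late enrollers get a fresh check; same-day rollovers do not.

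**Working it through.** The plan gives no figure to reproduce. There are three questions.

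**1. Does any entry rule apply the number to direct rollovers?**

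| Entry route | Rescreened | Numeric renal limit | Other renal control at entry |
|---|---|---|---|
| More than 14 days after the qualifying study | Yes | <40 mL/min (4.2.2) | 4.2.1 #4, #20 |
| Separate visit within 14 days | No (chemistry drawn) | None | 4.2.1 #4, #20 |
| Same day as end-of-study visit | No | None | 4.2.1 #4, #20 |

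The other half of the Section 1.2.5 sentence, on CYP3A4/5 inhibitors, does reach every subject, through 4.2.1 #17 and Appendix 3. Only the renal half stops at late enrollers.

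**2. Can the Appendix 4 creatinine rules stand in for the limit?**

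Inputs:
- Appendix 2 formula: clearance = (140 − age) × weight × factor / (72 × creatinine), with factor 1.00 for men and 0.85 for women.
- Retest (Appendix 4.1): rise >50% or >0.5 mg/dL, if indicated after review.
- Withdrawal (Appendix 4.3): two sequential rises >50% and >0.5 mg/dL.
- Reference for subjects entering within 14 days: the qualifying-study baseline.
- Assumptions: screening and baseline creatinine equal; age and weight constant.

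Neither rule fires if the rise is at most 50% and at most 0.5 mg/dL. With baseline creatinine c0, the largest unflagged value is min(1.5 × c0, c0 + 0.5). Clearance is inversely proportional to creatinine, so the baseline clearance from which an unflagged rise can just reach 40 mL/min is 40 × min(1.5, 1 + 0.5/c0). Anyone starting lower can pass below 40 unflagged.

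| c0 (mg/dL) | Calculation | Baseline clearance (mL/min) |
|---|---|---|
| 0.6 to 1.0 | 40 × 1.5 | 60.0 |
| 1.2 | 40 × 1.7/1.2 | 56.7 |
| 1.5 | 40 × 2.0/1.5 | 53.3 |
| 1.8 | 40 × 2.3/1.8 | 51.1 |

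Two illustrations with assumed patient values:
- Man, 70 years, 60 kg, creatinine 1.00 to 1.48 mg/dL: 70 × 60/(72 × 1.00) = 58.3, falling to 70 × 60/(72 × 1.48) = 39.4 mL/min. The rise is 48% and 0.48 mg/dL.
- Woman, 60 years, 70 kg, creatinine 1.2 to 1.7 mg/dL: 80 × 70 × 0.85/(72 × 1.2) = 55.1, falling to 80 × 70 × 0.85/(72 × 1.7) = 38.9 mL/min. The rise is 41.7% and exactly 0.5 mg/dL.

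Neither rule is met in either case. The creatinine rules contain no absolute floor, whereas the hematology and transaminase withdrawal rules include absolute or ULN-based limits.

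**3. What is the exposure at the entry dose?**

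Section 1.2.5 describes dose-proportional pharmacokinetics, so 5 mg BID scales directly:
- mild impairment: 5 × 1.37 = 6.85 mg BID equivalent;
- moderate: 5 × 1.43 = 7.15;
- severe: 5 × 2.25 = 11.25.

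The protocol does not map these categories to 40 mL/min. Just below the limit the moderate figure may apply; the severe figure is an upper bound.

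**The case against.** The strongest reply is that this is a wording mismatch in background text. Eligibility is set by Section 4, two-tier entry is stated design, and every numeric hematology, hepatic and renal exclusion sits in 4.2.2, so the renal limit follows the pattern. That explains where the criterion sits. It does not make the unqualified statement in 1.2.5 true for other entrants.

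Second, the harm looks modest. About 7.2 mg BID equivalent is below the 10 mg BID that the protocol permits and that both qualifying studies tested. This stands, and it limits the weight of the point. Escalation to 10 mg BID also requires that no laboratory abnormality is judged related to tofacitinib, so the main concern is exposure at the 5 mg BID entry dose.

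Third, other controls exist: criteria #4 and #20, the bar on subjects who stopped the qualifying study for treatment-related adverse events (injection-related ones excepted), chemistry at every treatment visit, and comparison with the qualifying-study baseline, which captures earlier drift. These narrow the group, but none supplies a clearance limit at entry. Stable low clearance need not count as uncontrolled disease.

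Fourth, the bounds above are worst cases. They show that the change rules are not a clearance floor; they do not show that anyone enters below 40.

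Fifth, Section 1.2.6 describes the PsA studies as recently completed and entry must occur within 3 months, so few rollovers may remain. Enrolment status is not stated. If recruitment has ended, correcting 1.2.5 is what remains useful.

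**Conclusion.** The concern holds. Section 1.2.5 describes a protection that the entry criteria do not provide for direct rollovers, and nothing else in the protocol supplies a renal number at entry on those routes. This should be corrected, but its likely reach is limited.

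The conclusion on the text rests on no assumption. The size does: about 7.2 mg BID equivalent at the entry dose assumes that the moderate-impairment figure applies just below 40 mL/min, and about 11.3 is an upper bound. The number of subjects affected cannot be estimated from these documents, because the qualifying studies' renal criteria are not given; it is probably small.

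**What to change.** Add estimated creatinine clearance <40 mL/min (Cockcroft-Gault, Appendix 2) to Section 4.2.1 so that it applies to all entrants. Assess it on the most recent qualifying-study creatinine available before first dose, or on the extension-study baseline value where one is available. This is an entry check only and adds no on-study clearance floor. If the sponsor intended the limit for late enrollers alone, Section 1.2.5 should say so and give the reason.

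The cost is one criterion and a calculation already defined in the protocol. No new test should be needed: Appendix 4 already relies on qualifying-study values, and chemistry is drawn at the separate within-14-day visit. A few rollovers may be excluded. For same-day rollovers the qualifying study's end-of-study schedule is not in these documents, so the value used may come from an earlier visit and could miss a recent decline.
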